9. WHO Recommendations for the Prevention and Treatment of Postpartum Haemorrhage. Geneva: World Health Organization; 2012.
10. WOMAN Trial Collaborators. Effect of early tranexamic acid administration on mortality, hysterectomy, and other morbidities in women with post-partum haemorrhage (WOMAN): an international, randomised, double-blind, placebo-controlled trial. Lancet. 2017 Apr 26.

Research Design:

a. General Approach: Prospective Cohort study

b. Description: Phase 4

c. Methods: One Arm

d. Statistical Analysis:

- SPSS software will be used for our statistical analysis. Normal distribution will be assumed given the intended number of patients for analysis. Categorical variables will be analyzed using the Chi-square test. The t-test will be utilized for the comparison of continuous interval data.

-Using postpartum hemorrhage rate of 2.86% (institutional data), and a desired impact of reducing the hemorrhage rates by 50% after implementation of the new protocol, then 890 subjects would need to be recruited to answer the question.

e. Safety Analysis Plan:

- Data collection for each participant will occur in real time during pre and post delivery times, therefore safety monitoring of the patient and data will be simultaneous.
- A Research monitor has been appointed to oversee the safe and ethical conduct of the study. Additionally, the Research Monitor will provide review and comment on any adverse events. The Research Monitor is not a member of the investigative team. The role of the Research Monitor is as follows:
 1. monitor the consent process to ensure an absence of coercion
 2. monitor data collection/clinical outcome
 3. review all adverse event reports with comments from the PI and forward to the IRB with his/her own comments. Adverse events must be received by the IRB within 5 business days of occurrence or reporting (within 24 hours for serious adverse events)
 4. ensure the inclusion/exclusion criteria are followed
 5. review data security measures
- Any emerging safety concerns to include any adverse event rate higher than this institution's historical average will result in a halt to the study.

Subject Population:

Pregnant women presenting for delivery at NMCSO

a. Exclusion/Inclusion criteria:

Exclusion:

- a. Age less than 18 years
- b. Planned cesarean hysterectomy
- c. Current anticoagulant use
- d. Subarachnoid hemorrhage
- e. Any active/current intravascular clotting (i.e. venous thromboembolic events)

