Informed consent will be obtained by members of the research team at any point during the subjects routine prenatal care visits.

Consent will only be obtained during a face-to-face communication in a confidential setting.

A member of the research team will provide a verbal and/or written information sheet giving a complete description of the rationale, goals, and requirements of the study. Participants will also be told of the volunteer nature of the study, and that they may cancel their participation in the study at any time, following the process outlined in the consent form.

The PI, AIs, or the research nurse will be available during the recruitment and enrollment phase of the trial. The PI/AI is available throughout the course of this trial. After reading the consent, having all questions answered to their satisfaction, and acknowledging understanding of what is involved in the trial, participants will be asked to sign the consent, along with the research team member obtaining the consent. A copy of the participant's signed consent will be given to them for their personal records.

All consents will include the participant's signature on the IRB-approved consent form. The participant will be given a copy of their signed consent form.

The original signed consent will be kept by the Clinical Research Nurse Coordinator in a locked cabinet in the office of the Clinical Research Nurse Coordinator.

Participants will be informed that they have the right to withdraw from this study at any time. If they decide to stop taking part in this study, they will be asked to tell the principle investigator as soon as possible.

Subject participation may be stopped without participant consent if remaining in the study might be dangerous or harmful in the investigator's opinion. It may also be stopped without participant consent if the military mission requires it, or if the participant loses the right to receive medical care at a military hospital.

Study Procedures:

1. Recruitment/Enrollment
 1. Identify subjects who meet inclusion criteria at prenatal registration, L&D tours, GDM classes, and on L&D
 2. Obtain written consent from potential participants after participant has had time to read, understand and comprehend
 3. "TXA Study Participant" to be added to problem list on hard chart, AHLTA template and ESSENTRIS intake
2. Implementation on L&D
 1. Re-identify patients on admission

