 2. For patients that present for delivery at a gestational age less than 34 weeks, it will be recommended that they discard their breast milk until 24 hours after their last TXA administration.
 3. Order TXA for patient in ESSENTRIS
 4. RN to pull TXA from Pyxis and put in patient's room
 5. TXA per protocol (see supplement A)
 6. The use of additional uterotonics or single additional dose of TXA is at the discretion of the delivering provider
 7. For patient monitoring protocol please see Supplement B.
 8. All neonates are monitored for a minimum of 24 hours either by the NICU or the Newborn Nursery. Vitals are taken every four hours. Weights and bilirubin levels are obtained daily. Daily physical exams are performed.
3. Data collection
 1. Participants will be assigned an individualized subject number upon their enrollment to the study.
 2. Participants will be followed from their enrollment into the study until six weeks postpartum.
 3. An Excel spreadsheet will be used to collect the variables as listed above.
 4. Once the variable collection is complete, the information will become de-identified.

5. Chart review will be performed to estimate institutional rates of the secondary outcomes in the 12 months preceding the initiation of the protocol.
4. Data Analysis
 1. SPSS software will be used for our statistical analysis. Normal distribution will be assumed given the intended number of patients for analysis. Categorical variables will be analyzed using the Chi-square test. The t-test will be utilized for the comparison of continuous interval data.
 2. Using a postpartum hemorrhage rate of 2.86% (institutional data), and a desired impact of reducing the hemorrhage rates by 50% after implementation of the new protocol, then 890 subjects would need to be recruited to answer the question.
 3. The secondary outcomes will also be tested against institutional rates. Institutional rates will be estimated by record sampling done at the time of data collection.

Experimental Procedures:

See supplement A

Research materials collected:

Variables to be collected:

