Age, race/ethnicity, DoD status, BMI, gestational age, # of fetuses, gravidity, parity, admission diagnoses, admission estimated fetal weight, intrapartum diagnoses, postpartum diagnoses, misoprostol use, oxytocin use, mechanical dilation, duration of labor, magnesium sulfate use, planned mode of delivery, mode of delivery, birth weight, indication for operative delivery, neonatal outcomes, maternal outcomes, admission to the intensive care unit, uterotonic use, mechanical tamponade, blood product transfusion, estimated blood loss, qualitative blood loss, cumulative blood loss, laboratory results, post-delivery laboratory results

Confounding variables:

Management of the 3rd stage of labor

Source of the data:

Outpatient records (AHLTA), Inpatient records (Essentris). As providers, the investigators have access to these systems as a standard of care for patients receiving care from investigator-providers.

Paper records created in the Labor and Delivery department during the course of a delivery.

The data collected will be measured against the historic PPH rates of NMCSO over a period of time to be determined.

Protection of Privacy:

Each participant will be given a unique study number. A master list with only the minimal Personal Identifiable Information (PII) needed for follow up and their study number will be kept in the PI's office on a CAC PIN protected computer in the PI's locked office. The master list will be used to track the results of the study participant's data collection.

An Excel spread sheet will be used to collect this information using only the participants unique study number and stored electronically on a CAC PIN protected computer in the PI's locked office.

All data and PII will be destroyed (shred or deleted) at the conclusion of this project.

Risks:

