To satisfy these two areas of responsibility, the research monitor may discuss the research protocol with the investigators, interview study subjects, and consult with others outside of the project about the research. In the event a problem is identified, they have authority to stop a research protocol in progress, remove individual subjects from a study, and take whatever steps are necessary to protect the safety and well-being of subjects until the IRB can assess the monitor's report.

Research monitors are required to promptly report their medical monitoring and oversight monitoring observations and findings to the IRB or other designated official.

Data Collection Sheets

See attached Excel spreadsheet.

Objectives:

The obstetrics literature to date focuses on TXA use prior to non-emergent cesarean delivery or in response to hemorrhage. Data is lacking in the area of prophylactic use prior to vaginal delivery. The aim of this study will be to assess the ability of TXA to prevent postpartum hemorrhage.

Primary Outcome:

To assess the efficacy of TXA in reducing the incidence of postpartum hemorrhage when given prophylactically prior to all deliveries.

The American Congress of Obstetricians and Gynecologists published 'ReVitalize' in 2014 that defined postpartum hemorrhage as blood loss of ≥ 1000 cc or blood loss accompanied by sign/symptoms of hypovolemia to include blood transfusion within 24 hours following the birth process (includes intrapartum loss).

[figure not shown]
For the purposes of this study, postpartum hemorrhage will be defined as a blood loss of ≥ 1000 cc in addition to all patients requiring blood transfusion (even if blood loss is less than 1000cc).

Secondary outcomes:

Estimated blood loss (EBL) – measured in cubic centimeters. EBL will be decided upon by the delivery provider. All delivering providers at this institution have received formal instruction on estimation of blood loss and a visual aid is available at every bedside and in the operating room (see below).

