Appendix L

Examples of Estimating Blood Loss

Zuckerwise. Estimated Obstetric Blood Loss With Visual Aid. *Obstet Gynecol* 2014.

Delivering providers will also adhere to NAVMEDWESTINST 6320.20, which specifies that once an EBL reaches 500cc, the delivering provider will move from an *estimation* of blood loss to utilizing a *quantitative* blood loss (QBL). QBLs are obtained by the weighing of chux pads, drapes, and linens that have been soiled (after first calibrating the scale to remove the original weight of the contaminated product). It also includes the blood that has been collected in the suction canister in the operating room.

In instances when EBL is decided upon at delivery, and ongoing bleeding occurs after the provider has left the room (and is called back), a QBL should be obtained. The QBL should be added to the initial EBL for a *cumulative* blood loss (CBL).

Percent decrease in hematocrit (Hct) – The percent change of the patients' Hct obtained on admission from that obtained after delivery. A post-operative Hct is routinely obtained six hours following a cesarean delivery. A Hct is not routinely obtained for patients having a vaginal delivery unless EBL exceeds 500cc. A post vaginal delivery Hct will not be obtained in patients for the sole purpose of this research study.

Rates of blood transfusion – The number of patients requiring blood transfusion divided by the total number of deliveries.

The types and amounts of products transfused – in patients requiring transfusion, the type of product (i.e, packed red blood cells, whole blood, fresh frozen plasma, platelets, and cryoprecipitate) will be recorded, along with how many of each type they received.

The use of uterotonic agents – in patients requiring uterotonic agents beyond the first bolus of oxytocin (i.e. second bolus of oxytocin, methylergonovine, 15-methyl Prostaglandin F_{2α}, misoprostol) will be recorded, along with how many doses of each

The need for surgical intervention – the number of patient's that require surgical intervention following a vaginal delivery for the purposes of controlling excessive blood loss divided by the total number of vaginal deliveries

The need for reoperation - the number of patients that require return to the operating room following a cesarean delivery for the purposes of controlling excessive blood loss divided by the total number of cesarean deliveries

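### Unmasked blood-loss estimates control both the primary outcome and the post-vaginal hematocrit, and no clean objective companion analysis is pre-specified

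*Combined protocol and SAP*

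**What the plan says.** Research Design gives the design as "c. Methods: One Arm". Under Source of the data: "The data collected will be measured against the historic PPH rates of" the institution, over a period still to be fixed. No placebo, masked assessor or independent review of blood loss is described.

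The delivering provider will know the treatment. Study Procedures, section 1, item 3 requires a study-participant label "to be added to problem list on hard chart, AHLTA template and ESSENTRIS intake", and section 2 has TXA ordered for each patient and placed in her room. Source of the data also refers to "patients receiving care from investigator-providers", so the assessor may be an investigator.

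Under Primary Outcome, PPH is a loss of at least 1000 cc, or any transfusion. Under Secondary outcomes, "EBL will be decided upon by the delivery provider", with formal training and a visual aid. The local instruction is one "which specifies that once an EBL reaches 500cc, the delivering provider will move from an" estimate to a weighed quantitative loss (QBL). If bleeding continues after the provider has left, a QBL is obtained and added to the initial estimate (EBL) to give a cumulative loss (CBL).

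Percent decrease in Hct is a named secondary outcome. "A post-operative Hct is routinely obtained six hours following a cesarean delivery". After vaginal birth an Hct is routine only when EBL exceeds 500 cc, and none will be added for research. Study Procedures, section 4, item 3 has the secondary outcomes tested against institutional rates, and section 3, item 5 plans a chart review of the preceding 12 months for them.

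**The concern.** One judgement, made by someone who knows the treatment and may expect it to work, does three things. It supplies the blood-loss figure, it decides whether the loss is weighed, and after vaginal birth it decides whether a laboratory value exists. The historic deliveries were assessed outside the study. If study estimates run lower for that reason, some women with a true loss of 1000 cc or more and no transfusion will not be counted, and the fall in PPH will partly reflect measurement.

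There are two main routes. A large loss may be estimated below 500 cc and never weighed, or the estimated part of a CBL may be too low. Few events are expected, so a modest number of missed cases matters.

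The natural cross-check is Hct. As the outcome is written, however, it combines cesareans, where measurement is routine, with vaginal births that enter only if the unmasked estimate passed 500 cc. A shift in estimation would change which vaginal births contribute, so the pooled comparison shares the problem it would be used to detect.

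**Working it through.** **Inputs.** From Research Design, Statistical Analysis: historic rate p0 = 0.0286; target reduction 50%, so p1 = 0.0143; n = 890; chi-square test. Alpha, sidedness and power are not stated. I assume two-sided 5% and 80% power because they reproduce the plan's figure.

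**The plan's sample size.** One-sample test against a fixed rate:

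n = [1.960·√(p0(1−p0)) + 0.8416·√(p1(1−p1))]² / (p0−p1)²
= [1.960 × 0.16668 + 0.8416 × 0.11872]² / 0.0143² = 889.99, so 890.

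One-sided 5% with 90% power gives 889, so the settings are not uniquely identified. A two-group comparison would need 1,611 per group, so 890 rests on treating 2.86% as fixed.

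**Number of events that decides the result.** Expected PPH with no TXA effect: 890 × 0.0286 = 25.45; SD = √(890 × 0.0286 × 0.9714) = 4.97.
- 15 events: z = (15 − 25.45)/4.97 = −2.10, p = 0.036.
- 16 events: z = −1.90, p = 0.057.

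A significant fall therefore needs 15 or fewer recorded events, about 10 below expectation.

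**Effect of under-recording.** Let m be the share of true PPH recorded as not PPH in the study period only. With no TXA effect the recorded rate is 0.0286(1−m). Against a fixed rate, the chance of a false significant fall is the binomial P(X ≤ 15 | 890, 0.0286(1−m)).

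The plan also says that historic rates will be sampled, so I repeated the calculation as an uncorrected two-sample comparison with an assumed historical cohort (200,000 simulated trials per cell). If the historical cohort shows exactly its expected rate, significance then needs 13 or fewer study events against 25 in 890 (p = 0.049), or 14 or fewer against 86 in 3,000 (p = 0.032).

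| Assumed m | Recorded PPH expected | Fixed 2.86% | 890 historical (assumed) | 3,000 historical (assumed) |
|---|---|---|---|---|
| 0% | 25.5 | 2% | 2% | 2% |
| 10% | 22.9 | 5% | 6% | 6% |
| 20% | 20.4 | 14% | 12% | 13% |
| 30% | 17.8 | 30% | 22% | 27% |
| 40% | 15.3 | 54% | 37% | 47% |

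**What limits m.** If the weighing rule is followed, an untransfused loss of 1000 cc or more at delivery escapes weighing only if estimated below 500 cc, an error of more than half (500/1000). Transfused women count whatever their estimate. The remaining route is the estimated part of a CBL. The documents give neither the share of PPH without transfusion nor the accuracy of EBL, so m cannot be narrowed further from them.

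**The case against.** The best defence is that the plan already contains safeguards. Providers are trained and have a visual aid. Weighing begins at half the PPH threshold, later bleeding requires a QBL, and every transfusion counts. Hct change, transfusion, reoperation, hysterectomy and ICU admission are all secondary outcomes to be compared with institutional rates.

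Much of this stands. A reader might infer that the routine cesarean Hct is not used, or that nothing in the planned analysis could reveal biased estimation. The documents do not support either: Hct change is a named outcome that draws on that measurement, and a PPH fall with flat Hct and transfusion could be seen.

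A reader might also infer that expectation alone, or a small downward lean, would produce a positive result. The table does not show that. At 10% under-recording the chance is 5% to 6%, and it passes one half only near 40%, and then only against a fixed rate. Nothing in the documents says that 30% or 40% is plausible.

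What the defence does not answer is that training leaves the assessor unmasked, the weighing safeguard starts with the judgement in question, and the Hct outcome as defined admits vaginal births through that same judgement.

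**Conclusion.** The concern holds in a limited form. An unmasked estimate determines weighing and post-vaginal Hct, so untransfused PPH can be under-recorded relative to the historic period. The existing safeguards reduce this without removing it. The Hct outcome is present but, as pooled, is not a clean objective check on the primary result.

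With no TXA effect, the chance of a significant fall rises from about 2% to 12–14% at 20% under-recording and to 37–54% at 40%, depending on the comparator. This rests on an inferred two-sided 5% test, 890 evaluable deliveries, assumed historical cohort sizes, and under-recording confined to the study period. The under-recording fractions are illustrative.

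The documents do not say whether the 2.86% was obtained under the same estimate-then-weigh rule. If it was not, the comparison could be biased whatever providers expect.

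A strict rule that Hct and transfusion must both move in the same direction as PPH before efficacy is claimed would go too far. With no TXA effect, the transfusion rate would fall below its expected value about half the time by chance, so direction alone is weak evidence.

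**What to change.** Add to the analysis section, before outcome data are examined:

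1. The admission-to-6-hour Hct fall among all cesareans, study against historical period, is the pre-specified objective companion to the primary outcome. It is reported beside the PPH result with a confidence interval, together with the transfusion rate and its interval.
2. Hct values after vaginal birth, which exist only when EBL exceeded 500 cc, are not pooled with the cesarean values. If shown, they are shown separately and described as selected.
3. If PPH falls and these measures do not accompany it, the report will name unmasked assessment of blood loss as a possible explanation.

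Study Procedures, section 2, item 6 says "The use of additional uterotonics or single additional dose of TXA is at the discretion of the delivering provider", so uterotonic use depends on the same unmasked provider and is not part of this companion analysis.

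Cost: no added test, visit or participant. Admission and 6-hour Hct must be abstracted for historical cesareans within the chart review already planned for the preceding 12 months. That is somewhat more work than the record sampling now described. The documents do not confirm that both values exist for every historical cesarean, so completeness in each period should be reported. The main limitation is that the check does not cover vaginal births, where the Objectives section says prophylaxis data are lacking.

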- f. Patients with a hypersensitivity to TXA or any of the ingredients

- g. History of venous or arterial thrombotic events because use of tranexamic acid is a risk factor for thromboembolism.
- h. Conditions that predispose patients to thromboembolic events (e.g. thrombophilias, autoimmune diseases such as lupus, active cancer, congestive heart failure) because of increased risk of thrombosis
- i. Patients taking factor IX complex concentrates or anti-inhibitor coagulant concentrates (e.g. FEIBA NF)
- j. Seizure disorder because the use of tranexamic acid has been associated with postoperative seizures
- k. Patients with a baseline creatinine 1.2 or higher, history of renal insufficiency, or renal disease because of the risk of toxicity in patients with preexisting disease.
- l. Patients with frank hematuria because ureteral obstruction due to clot formation has been reported in patients with upper urinary tract bleeding who were treated with tranexamic acid
- m. History of retinal disease as cases of central retinal artery and vein obstruction have been reported in patients treated with tranexamic acid
- n. Patients with acquired defective color vision
- o. Patients with retinal diseases; cases of central retinal artery and central retinal vein obstruction have been reported in patients treated with intravenous tranexamic acid.

Inclusion:

-Pregnant women 18-54 years old delivering at Navy Medical Center San Diego (NMCS D)

Recruitment Process:

Patients will be identified in the antenatal clinics of Naval Medical Center San Diego. All patients that meet the inclusion criteria will be offered inclusion in the study.

All English speaking women who are eligible to receive care at NMCS D and presenting to NMCS D's Labor and Delivery Unit, who are at least 18 years old, not older than 54, and who are scheduled to deliver at NMCS D, will be given verbal and/or a written information sheet about the study and a description of what the study entails. OBGYN staff providers and residents will also be given an information sheet about the study. Opportunities for potential participant recruitment include:

- NMCS D Prenatal Registration
- NMCS D Gestational Diabetes education classes
- NMCS D Labor and Delivery tour of the unit

Subject eligibility and screening will take place prior to offering potential subjects the opportunity to participate in the study. An eligibility and screening tool will be used as part of the recruitment process.

Consent Process:

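### The t-test for provider-estimated blood loss ignores clustering by provider, so its standard error is too small if more than a few providers, or their caseloads, change between periods

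*Combined protocol and SAP*

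**What the plan says.** Under Secondary outcomes, the EBL paragraph states that "EBL will be decided upon by the delivery provider". It adds at once that "All delivering providers at this institution have received formal instruction on estimation of blood loss and a visual aid is available at every bedside", and the operating room has the aid too. The text after the visual aid (Appendix L) sets a further safeguard: "once an EBL reaches 500cc, the delivering provider will move from an" estimated to a weighed figure. Bleeding that continues after the provider has left is also to be measured quantitatively and added to the initial estimate.

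The analysis rule, given under Research Design and again under Study Procedures (Data Analysis), is "The t-test will be utilized for the comparison of continuous interval data". No provider term, clustering or robust variance is mentioned. The design has one arm. On the comparator the plan says "The secondary outcomes will also be tested against institutional rates", and under Data collection "Chart review will be performed to estimate institutional rates of the secondary outcomes in the 12 months preceding the initiation of the protocol". The number of historic records is not given.

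The list under Research materials collected includes "estimated blood loss, qualitative blood loss, cumulative blood loss" and mode of delivery, but not the delivering provider. Third-stage management is the only confounder named. On who the providers are, the Recruitment Process section says "OBGYN staff providers and residents will also be given an information sheet about the study". No section gives their number or says whether the same people work in both periods.

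**The concern.** A visual estimate carries the habits of the person making it. Two women delivered by the same provider share that person's tendency to read high or low, so their EBL values are not independent, as the t-test assumes.

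If each provider treated women in both groups at the same time, these tendencies would largely cancel. Here one group delivers before the protocol starts and the other after, so they cancel only if the same people deliver similar shares of the women in both periods. Otherwise the t-test treats a change in who is estimating as evidence about tranexamic acid. Its p-value and interval for EBL would then be too optimistic, and the listed variables contain nothing with which to correct them.

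**Working it through.** **The plan's own figure.** The only sample size is 890, for postpartum hemorrhage at 2.86% reduced by half to 1.43%. Alpha and power are not stated. A one-sample test against a fixed rate, two-sided 5% with 80% power, gives

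n = [1.960·√(0.0286·0.9714) + 0.8416·√(0.0143·0.9857)]² / 0.0143² = 889.99, so 890.

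(One-sided 5% with 90% power gives 889.) The figure concerns the primary outcome. It treats the historic rate as fixed, so it gives no historic sample size and no information on EBL.

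**Inputs for EBL.** From the documents: 890 study women. Assumed, because the documents are silent: n₀ = 300 to 890 historic records, J = 30 to 60 providers in each period, a share ρ = 0.02 to 0.10 of EBL variance between providers, and a fraction f of providers replaced. The test is taken as a two-sample t-test on individual records.

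**Formula.** Let provider j deliver share p_j of the historic women and q_j of the study women. The true variance of the mean difference, divided by the variance the t-test uses, is approximately

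R = (1 − ρ) + ρ·Σ(p_j − q_j)² / (1/890 + 1/n₀).

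A change in caseloads among the same providers enters through the same sum as turnover does. With equal caseloads and a fraction f replaced, the sum is 2f/J, so

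R = (1 − ρ) + ρ·f·m, where m = H/J and H = 2/(1/890 + 1/n₀).

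If caseloads also vary by chance, the sum grows by about 1/890 + 1/n₀, and R = 1 + ρ·f·m. The true error of a nominal 5% test is 2[1 − Φ(1.96/√R)].

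**Numbers.** H = 890 for n₀ = 890, and H = 2·890·300/1190 = 448.7 for n₀ = 300.
- Mild corner: J = 60, ρ = 0.02, n₀ = 300, so m = 448.7/60 = 7.48.
- Severe corner: J = 30, ρ = 0.10, n₀ = 890, so m = 890/30 = 29.67.

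With chance variation in caseloads:

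| Replaced | R, mild | Error | R, severe | Error |
|---|---|---|---|---|
| none | 1.000 | 5.0% | 1.000 | 5.0% |
| one third | 1.050 | 5.6% | 1.989 | 16.5% |
| half | 1.075 | 5.9% | 2.483 | 21.4% |
| all | 1.150 | 6.8% | 3.967 | 32.5% |

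Simulation of the t-test (8,000 runs per setting) gave 5.4%, 5.8% and 6.2% in the mild corner and 16.1%, 21.7% and 32.7% in the severe corner for one third, half and all replaced.

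**A middle case.** With 890 women in each period, 40 providers, ρ = 0.05 and equal caseloads, m = 22.25. At 25%, 50% and 100% replaced, R is 1.228, 1.506 and 2.062. The true standard error is 1.11, 1.23 and 1.44 times the t-test's, and the error is 7.7%, 11.0% and 17.2%.

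**Where the problem starts.** With equal caseloads, R exceeds 1 only when f exceeds 1/m. That is 1/29.67 = 3.4%, about one provider of 30, in the severe corner. In the mild corner it is 1/7.48 = 13.4%, about eight of 60. Below that point the t-test is slightly conservative: with no replacement R = 1 − ρ, and the error is 3.9% to 4.8%.

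**The case against.** The plan already acts on the quantity that drives the result. Providers are trained, a visual aid is at hand, and weighing takes over at 500 cc. All of this should lower ρ. The objection stands in part: the mild corner may be nearer the truth, but nothing in the documents shows that ρ is zero. Below 500 cc the value remains a judgment, and the provider's own estimate triggers the weighing.

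The two periods may adjoin at one hospital, and no section reports any turnover. That residents are among the providers does not show how many leave. This also stands, and full turnover is an outer limit, not an expectation.

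The provider term would not address the larger weaknesses of a one-arm historic comparison. Providers know that the drug is given, and estimation may drift over time. Both can act within every provider, so a random intercept does not remove them. This is correct and limits what the change can achieve.

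Three stronger readings are tempting and not supported:
- A reader might infer that intervals are too narrow whenever any provider changes. With equal caseloads the effect begins only beyond the break-even fraction.
- A reader might infer that the provider cannot be identified. The data sheet is not shown, and the delivery records used as source may name the provider.
- A reader might infer that the primary result is compromised. The primary outcome is categorical and not analyzed by this t-test, and its 1000 cc threshold lies in the range where blood loss is to be weighed.

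**Conclusion.** The point holds in a conditional form and for a secondary outcome only. With stable providers and caseloads, the planned t-test for EBL has about its nominal error. If more than a few providers change, or caseloads shift materially among the same providers, its standard error is too small. Under the stated assumptions the inflation runs from negligible (5.6% with one third replaced, mild corner) to serious (about 33% with all replaced, severe corner). The documents cannot place the trial within that range, because provider number, turnover, between-provider variance and historic sample size are all missing. The change is worth making because it is cheap and does little harm if it proves unnecessary.

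**What to change.** Add a coded delivering-provider identifier to both the participant data sheet and the historic chart-review sheet, using the same codes. Do this before the data are de-identified, since linking provider to delivery is harder afterwards.

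Replace the t-test for EBL by a linear mixed model with cohort and mode of delivery as fixed effects and provider as a random intercept. Mode of delivery is already collected for participants and must also be taken from the historic charts. It belongs in the model because a provider effect could otherwise absorb differences between cesarean and vaginal caseloads. Providers who work in both periods then contribute a within-provider comparison. Provider-clustered standard errors are a simpler alternative.

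The cost is one extra column on each sheet and one sentence of analysis text; SPSS fits the model. The confidence interval will be somewhat wider if providers have turned over. The plan should also state that this corrects for provider clustering only, not for unblinded estimation or drift over time.
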